#### **6.5 Overdose**

All occurrences of overdose must be reported as SAEs (see [Section 6.1.1](#) for reporting details).

An overdose is defined as the accidental or intentional administration of any dose of a product that is considered both excessive and medically important. All occurrences of overdose must be reported as an SAE (see [Section 6.1.1](#) for reporting details.).

#### **6.6 Adverse Events of Interest**

Adverse events of interest are AEs consistent with an immune mediated mechanism and include enterocolitis, dermatitis, hepatitis, endocrinopathies and neuropathies, although other less common immune mediated AEs have been reported as well. The severity of these immune mediated AEs may range from mild to severe and life threatening.

These AEs of interest will be evaluated as follows:

- **Immune-related adverse events (irAEs):** These are AEs that are 1) AEs of interest (per description above) and 2) drug related by the investigator.
- **Immune-mediated adverse reactions (imARs):** AEs of special interest will also be adjudicated by the investigator as an imAR (yes) or not an imAR (no) or unknown. The rationale for imAR adjudication is in [Section 1.4.1](#).

The characterization of an AE as an imAR or not is based on retrospective review of the AE that takes into account the context (eg, concomitant therapies, medical history, etc), evaluation, treatment and outcome. Therefore, for purposes of managing an AE, the investigator should refer to the guidance in the protocol (provided in [Section 4.3](#)) and Investigator Brochure for evaluation and treatment and not use the case definitions. Data relative to these evaluations and interventions must be included in the source documentation. The complete case definitions for classifying AEs as an imAR are provided as an Appendix in the IB, however in general:

1. AEs of interest should first be evaluated for exclusion as an imAR:
  - Typical reasons an event is not considered an imAR
    - Likely due to concomitant drug/chemotherapy/radiation and thus unlikely an imAR
    - Documented evidence of tumor, tumor progression, or tumor related as the most likely cause of the event
    - Same grade event at baseline/medical history/pre-treatment event
    - Event likely caused by infection, or other disease process (eg, infection) or etiology
    - Resolves in less than 1 week without immunosuppression (a definition based on review of resolution for immune mediated AEs of interest from ipilimumab program) suggests that the AE is not an imAR
    - Other reasons may also be valid (see Investigator Brochure, Case Definitions).
2. If the investigator is unable to exclude then the AE of interest should be evaluated as an imAR:
  - Typical reasons an event is considered an imAR:
    - Inflammation per pathology or endoscopy
    - Radiologic, imaging, laboratory, or other diagnostic procedure the provides or suggest evidence of an inflammatory process
    - Improves/resolves after immunosuppression (eg, favorable evolution when treated by immunosuppressive drugs supports the AE to be an imAR.)
    - Similar to previous imAR in same organ (based on clinical data from ipilimumab program that imARs may recur in same organ
    - Other reasons may also be valid such as AE persists greater than 1 week or worsens (see Investigator Brochure, Case Definitions).

Occasionally, AEs of interest will not have enough information to classify as imAR or not, in which case, the AE should be classified as unknown whether imAR.

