### **1.4.1 Assessment of Immune-Mediated Adverse Reactions**

The safety profile of ipilimumab has historically been described by irAEs, which are defined as 1) AEs that are related to ipilimumab per investigator and 2) are consistent with an inflammatory process. Recently, BMS conducted an independent, retrospective adjudication of AEs from two randomized Phase 3 trials (MDX010-20 and CA184024). Adjudication of AEs was limited to the common target organs of ipilimumab toxicity (eg, enterocolitis, hepatitis, dermatitis, endocrinopathy) or other less common AEs that may be immune-mediated (eg, neuropathy) and was conducted in a blinded fashion to investigator attribution (eg, irAE). The AEs were adjudicated as being immune mediated or not immune-mediated based on case definitions for ipilimumab-related AEs developed from 1) guidance for evaluation of AEs of interest provided to investigators and 2) review of irAE outcomes and treatments in the Phase 2 and 3 program.

Classification of a potential AE as an immune-mediated adverse reaction (imAR) using these case definitions (provided in the Investigator Brochure) was based on first excluding as imAR based on

- 1) alternative, non-immune-mediated etiology (eg, tumor progression, infection, concomitant medication/radiation), or
- 2) unlikely to be immune mediated from ipilimumab based on the behavior of the AE (eg, rapidly resolves without need for immunosuppression).

AEs that could not be excluded as above were then evaluated as “**possibly**” (eg, AE persists > 1 week, previous imAR in same organ) or “**definitely**” (eg, biopsy proven inflammation) imARs. Occasionally, AEs were classified as “**unknown**” due to insufficient information. For summary purposes, AEs were grouped as: not-imAR (excluded as imAR) or an imAR (unknown, definitely, possibly).

As summarized in Table 1.4.1-1, imAR adjudication in MDX010-20 was specific and sensitive for detection of immune mediated AEs since the control arm had a very low rate of ‘imARs’. Henceforth, imAR adjudication will be performed by the investigator and not the Sponsor.

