### **2.3 Blinding and Unblinding**

Not applicable (open-label study).

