## **7.6 Safety**

Summaries of safety will be based on all treated subjects by treatment arm, except for the resource utilization (based on all randomized subjects).

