### **Immune-Mediated Adverse Reactions**

Summaries of imARs will be based on all treated subjects.

The following summaries for on-study phase imARs will be provided (for subcategories as specified in the core imAR SAP):

- Summary of subjects with worst grade of grade 2 on-study phase imAR
- Summary of subjects with worst grade of grade 3-4 on-study phase imAR

- Summary of subjects with worst grade of grade 5 on-study phase imAR
- Summary of subjects with worst grade of grade 2-5 on-study phase imAR and outcome of hospitalization by subcategory (worst CTC grade [2+, 3-4, 5] by subcategories)
- Summary of subjects with worst grade of grade 2-5 on-study phase imAR who received blood transfusion by subcategory (worst CTC grade [2+, 3-4, 5] by subcategories)
- Time to first onset (any grade) of imARs for subjects with worst grade of grade 2-5 on-study phase imAR by subcategory
- Time to resolution of imARs for subjects with worst grade of grade 2-5 on-study phase imARs by outcome of resolution by subcategory
- Time to resolution of imARs for subjects with worst grade of grade 2-5 on-study phase imARs by use of systemic corticosteroids and outcome of resolution by subcategory
- Time to resolution of imARs for subjects with worst grade of grade 2-5 on-study phase imARs by use of high dose systemic corticosteroids and outcome of resolution by subcategory
- Time to resolution of imARs for subjects with worst grade of grade 2-5 on-study phase dermatitis imARs by use of topical corticosteroids and outcome of resolution
- imARs leading to study drug discontinuation by use of high dose systemic corticosteroids for subjects with worst grade of grade 2-5 imARs, by subcategory
- Distribution of outcome (last reported grade) of imARs for subjects with worst grade of grade 2-5 on-study phase imARs by subcategory
- Distribution of outcome (last reported grade) of imARs for subjects with worst grade of grade 2-5 on-study phase imARs by use of systemic corticosteroids by subcategory
- Distribution of outcome (last reported grade) of imARs for subjects with worst grade of grade 2-5 on-study phase imARs by use of high dose systemic corticosteroids by subcategory
- Distribution of outcome (last reported grade) of imARs for subjects with worst grade of grade 2-5 on-study phase dermatitis imARs by use of topical corticosteroids
- Distribution of outcome (last reported grade) of imARs for subjects with worst grade of grade 3-5 on-study phase imARs by subcategory

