## **APPENDIX 1      IMMUNE-RELATED ADVERSE EVENT SEARCH CRITERIA VERSION 20.0 (APRIL 2017)**

The following MedDRA terms (**MedDRA version 20.0**) will be used for generating irAE AEs/SAEs among all adverse events reported by investigators as possibly, probably or certainly related or with unknown causality (PTs from primary SOC will be used for multi-category PTs with exception as noted).

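### The by-arm irAE and imAR tables in SAP 7.6.1 rest on unblinded investigator attribution, and no visible table shows the same target-organ categories regardless of causality

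*Protocol*

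**What the plan says.** - **Setting.** SAP 2.3 records that blinding does not apply because the study is open-label. SAP 7.6 states: "Summaries of safety will be based on all treated subjects by treatment arm"; only resource utilization is excepted. SAP 7.6.1 uses the same population for irAEs and repeats it for imARs: "Summaries of imARs will be based on all treated subjects".
- **irAE.** Protocol 6.6 defines irAEs thus: "These are AEs that are 1) AEs of interest (per description above) and 2) drug related by the investigator". SAP Appendix 1 applies a MedDRA list "among all adverse events reported by investigators as possibly, probably or certainly related or with unknown causality". Neither limits the drug to ipilimumab, and protocol Section 4 counts comparators among the study drugs. The list includes non-infective diarrhoea, stomatitis, alopecia and hepatic enzyme terms. Protocol 1.4.1, describing historical use, instead ties irAEs to ipilimumab.
- **imAR.** Protocol 1.4.1: "Henceforth, imAR adjudication will be performed by the investigator and not the Sponsor". Protocol 6.6 has the investigator look first for a reason to exclude. One typical reason is "Likely due to concomitant drug/chemotherapy/radiation and thus unlikely an imAR"; another disease process or cause is also listed. Protocol 1.4.1 foresees that an event may be drug-related and still not an imAR, with concomitant chemotherapy as its example.
- **Tables that do not use attribution.** SAP 7.6.1 plans all-causality AE and SAE tables by SOC and exposure-adjusted rates of AEs occurring in at least 5% of subjects. SAP 7.6.2 plans worst laboratory grades, including liver function, and SAP 7.6.3 plans deaths.

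**The concern.** Ipilimumab toxicity is expected in particular organs: bowel, liver, skin, endocrine glands and nerves. A reader comparing the arms on those organs will go to the irAE and imAR tables, because in the visible SAP 7.6.1 only these are grouped that way. Both have passed through a judgement made with knowledge of the arm. For a chemotherapy control the two judgements can also disagree about the same event: attribution to DTIC brings it into the irAE count and gives a reason to leave it out of the imAR count. If so, the two tables could give different pictures of the ipilimumab excess. No table by the same categories would show how much of that difference comes from events and how much from attribution.

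**Working it through.** **1. One listed event followed through each definition.**

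| Rule | On DTIC, attributed to DTIC | On ipilimumab, attributed to ipilimumab |
|---|---|---|
| irAE, protocol 6.6 and SAP Appendix 1 | counted | counted |
| irAE, protocol 1.4.1 (related to ipilimumab) | not counted | counted |
| imAR, protocol 6.6 and 1.4.1 | can be excluded as due to chemotherapy or another non-immune cause | no study chemotherapy to cite; other exclusions remain, otherwise assessed as an imAR |

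So the irAE result for a DTIC event depends on which definition is applied. Under the operative one, the same event can be in one table and out of the other.

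**2. Why SOC tables do not fill the gap.** Appendix 1 categories are selected HLGTs, HLTs and PTs with named exceptions, so they do not coincide with SOCs. Subject counts also cannot be added across rows. Table 1.4.1-1 shows this for ipilimumab 3 mg/kg:

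- Grade 2 by organ: 7 + 8 + 25 + 1 + 6 + 3 = 50
- Severe by organ: 9 + 1 + 3 + 1 + 5 + 1 = 20
- Sum over organs: 70, against 34 + 19 = 53 over all types

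Adding rows overstates the number of subjects affected, because one subject can appear in several.

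**3. The reference figures in the documents (Table 1.4.1-1, MDX010-20).** Grades 3, 4 and 5 on ipilimumab add to the severe row (16 + 2 + 1 = 19), so rows are taken as worst grade and Grade 2 plus severe as Grade 2 or higher.

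- Ipilimumab: (34 + 19)/131 = 53/131 = 40.5%
- gp100: (11 + 1)/132 = 12/132 = 9.1% (exact 95% CI 4.8 to 15.3%)
- Difference: 40.5 − 9.1 = 31.4 points

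The printed severe rate for gp100, 1/132 = 0.8%, reproduces. One cell does not: ipilimumab Grade 2 hepatotoxicity, 8/131 = 6.1%, is printed as 5.3%. The 31.4 points do not use it.

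**4. What attribution could do, on assumptions only.** The documents give no DTIC event rates and no attribution probabilities.

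- *imAR, using the gp100 background.* Suppose the DTIC arm had the same 9.1%, the ipilimumab rate stayed fixed, and half or all control events were excluded. The control rate becomes 4.5% or 0%, and the difference 40.5 − 4.5 ≈ 35.9 (unrounded rates) or 40.5 points.
- *irAE, equal true rates.* Let a share e of each arm have a listed event, called related with probability a_I on ipilimumab and a_D on DTIC. The spurious difference is e × (a_I − a_D). With e = 0.40, a_I = 0.9 and a_D = 0.6 it is 0.40 × 0.3 = +12 points; with the probabilities exchanged, −12; with both at 0.9, 0.
- *imAR, equal true rates.* With e = 0.40 and 80% of ipilimumab events kept, the spurious difference is 0.40 × (0.8 − 0.8) = 0 if 80% of DTIC events are kept, and 0.40 × (0.8 − 0) = 32 points if none are.

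The irAE distortion can take either sign, and the imAR distortion runs from none to large. Nothing in the documents chooses among these values.

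**The case against.** Several counter-arguments have force.

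- **The exclusion wording.** It speaks of concomitant chemotherapy and is only a typical reason; DTIC was the comparator, not concomitant therapy. This stands: a DTIC event can be excluded, most directly under the broader non-immune-cause exclusions, but the visible text does not say that it will be.
- **The purpose of the imAR.** It is meant to remove non-immune toxicity, so a low control rate is partly intended. This stands. The weakness is that the judgement is unblinded and may follow the arm.
- **Attribution-free tables exist.** A reader might infer that no planned table uses one event definition in both arms. That is wrong, as the SOC, laboratory and death tables show. The gap is confined to target-organ categories.
- **Exclusions are visible.** SAP 7.6.1 plans a listing for all regimens of events adjudicated yes, no or unknown, with reasons. This helps, but a listing does not give a by-arm subject count.
- **Opposite biases.** A reader might infer that the irAE table understates and the imAR table overstates the ipilimumab excess. The calculations above show that the irAE sign is open, and no passage shows wrongful exclusion on DTIC.
- **The MDX010-20 adjudication.** A reader might infer that it was blinded to arm. Protocol 1.4.1 says only that it was blinded to investigator attribution. It remains true that its specificity was argued from a non-chemotherapy control.
- **Text not seen.** SAP 4.3.1.1 is not in the public text, and the core imAR SAP and Investigator Brochure case definitions are separate documents. Any of them may say how DTIC events are handled, so no claim is made that such a rule is absent.

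**Conclusion.** The concern holds in a limited form. The by-arm irAE and imAR tables depend on unblinded investigator attribution. Under the operative definitions a DTIC-attributed event can enter the first and be ruled out of the second. The visible SAP 7.6.1 has no all-causality table by target-organ category to set beside them.

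Neither direction nor size of bias can be determined. Only the 31.4-point difference comes from the documents, and it belongs to another trial with another control; the 35.9, 40.5, ±12 and 32-point figures are illustrations.

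A reader might infer that neither comparison is fair. The documents do not support that: they show dependence on attribution, not a demonstrated distortion. No test is specified for these tables, and the objectives in SAP Section 3 include no safety comparison, so the efficacy conclusions are untouched.

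The verdict assumes that protocol 6.6, read here in Revised Protocol 04, matches the Revised Protocol 03 text that SAP version 2.0 reflects. The summary of changes does not list Section 6.6, which makes this likely.

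**What to change.** 1. In SAP 7.6.1, add supplementary by-arm tables of the Appendix 1 terms regardless of causality: any grade, 3-4 and 5, by GI, liver, skin, endocrine, neurological and other. Read them alongside the irAE and imAR tables when arms are compared, not in their place.
2. Footnote the irAE and imAR tables as dependent on unblinded investigator attribution.
3. Reconcile the irAE definition in protocol 1.4.1, tied to ipilimumab, with those in protocol 6.6 and SAP Appendix 1, which are not.

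The cost is a re-run of the subcategory programs without the causality filter, plus wording; no new data are needed. The new tables carry more background noise and still include non-immune chemotherapy effects such as alopecia: they remove the dependence on attribution, not the non-specificity of the list. Because the database was locked on 03Jun2019, they must be labelled post hoc.

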## **6.7 Other Safety Considerations**

Any significant worsening noted during interim or final physical examinations, electrocardiogram, x-ray filming, any other potential safety assessment required or not required by protocol should also be recorded as a nonserious or serious AE, as appropriate, and reported accordingly.

## **7 DATA MONITORING COMMITTEE AND OTHER EXTERNAL COMMITTEES**

Not Applicable.

## **8 STATISTICAL CONSIDERATIONS**

### **8.1 Sample Size Determination**

There are two patients eligible for Re-induction.

### **8.2 Populations for Analyses**

No analysis will be conducted.

### **8.3 Endpoints**

Not applicable.

#### **8.3.1 Safety**

Safety data need to be collected until 90 days after the last dose of study medication is received.

### **8.4 Analyses**

#### **8.4.1 Efficacy Analyses**

Not applicable.

#### **8.4.2 Safety Analyses**

No safety analysis will be conducted.

#### **8.4.3 Pharmacokinetic Analyses**

Not applicable.

#### **8.4.4 Biomarker Analyses**

Not Applicable.

#### **8.4.5 Outcomes Research Analyses**

Not Applicable.

#### **8.4.6 Other Analyses**

Not Applicable.

#### **8.4.7 Interim Analyses**

Not applicable.

## **9 STUDY MANAGEMENT**

### **9.1 Compliance**

#### **9.1.1 Compliance with the Protocol and Protocol Amendment**

The study shall be conducted as described in this approved protocol. All revisions to the protocol must be discussed with, and be prepared by, BMS. The investigator should not implement any deviation or change to the protocol without prior review and documented approval/favorable opinion from the IRB/IEC of an amendment, except where necessary to eliminate an immediate hazard(s) to study subjects.

If a deviation or change to a protocol is implemented to eliminate an immediate hazard(s) prior to obtaining IRB/IEC approval/favorable opinion, as soon as possible the deviation or change will be submitted to:

- IRB/IEC for review and approval/favorable opinion
- BMS
- Regulatory Authority(ies), if required by local regulations

Documentation of approval signed by the chairperson or designee of the IRB(s)/IEC(s) must be sent to BMS.

If an amendment substantially alters the study design or increases the potential risk to the subject: (1) the consent form must be revised and submitted to the IRB(s)/IEC(s) for review and approval/favorable opinion; (2) the revised form must be used to obtain consent from subjects currently enrolled in the study if they are affected by the amendment; and (3) the new form must be used to obtain consent from new subjects prior to enrollment.

If the revision is done via an administrative letter, investigators must inform their IRB(s)/IEC(s).

#### **9.1.2 Monitoring**

Representatives of BMS must be allowed to visit all study site locations periodically to assess the data quality and study integrity. On site they will review study records and directly compare them with source documents, discuss the conduct of the study with the investigator, and verify that the facilities remain acceptable.

In addition, the study may be evaluated by BMS internal auditors and government inspectors who must be allowed access to source documents, other study files, and study facilities. BMS audit reports will be kept confidential.

The investigator must notify BMS promptly of any inspections scheduled by regulatory authorities, and promptly forward copies of inspection reports to BMS.

#### **9.1.3 Investigational Site Training**

Bristol-Myers Squibb will provide quality investigational staff training prior to amendment initiation. Training topics will include but are not limited to: GCP, AE reporting, study details

and procedure, study documentation, drug ordering, safety reporting, informed consent, and enrollment of WOCBP.

## **9.2 Records**

### **9.2.1 Records Retention**

The investigator must retain all study records and source documents for the maximum period required by applicable regulations and guidelines, or institution procedures, or for the period specified by BMS, whichever is longer. The investigator must contact BMS prior to destroying any records associated with the study.

BMS will notify the investigator when the study records are no longer needed.

If the investigator withdraws from the study (eg, relocation, retirement), the records shall be transferred to a mutually agreed upon designee (eg, another investigator, IRB). Notice of such transfer will be given in writing to BMS.

### **9.2.2 Study Drug Records**

It is the responsibility of the investigator to ensure that a current disposition record of investigational product (those supplied by BMS) is maintained at each study site where study drug is inventoried and dispensed. Records or logs must comply with applicable regulations and guidelines and should include:

- drug order form
- amount received and placed in storage area
- amount currently in storage area
- label identification number or batch number
- amount dispensed to and returned by each subject, including unique subject identifiers
- amount transferred to another area/site for dispensing or storage
- nonstudy disposition (eg, lost, wasted)
- amount destroyed at study site, if applicable
- amount returned to BMS
- retain samples for bioavailability/bioequivalence, if applicable
- dates and initials of person responsible for Investigational Product dispensing/accountability, as per the Delegation of Authority Form.

### **9.2.3 Case Report Forms**

An investigator is required to prepare and maintain adequate and accurate case histories designed to record all observations and other data pertinent to the investigation on each individual treated or entered as a control in the investigation.

The confidentiality of records that could identify subjects must be protected, respecting the privacy and confidentiality rules in accordance with the applicable regulatory requirement(s).

### **9.3 Clinical Study Report and Publications**

A Signatory Investigator must be selected to sign the clinical study report.

For this protocol, the Signatory Investigator will be selected considering the following criteria:

- External Principal Investigator designated at protocol development
- National Coordinating Investigator
- Study Steering Committee chair or their designee
- Subject recruitment (eg, among the top quartile of enrollers)
- Involvement in trial design
- Regional representation (eg, among top quartile of enrollers from a specified region or country)
- Other criteria (as determined by the study team).

The data collected during this study are confidential and proprietary to BMS. Any publications or abstracts arising from this study must adhere to the publication requirements set forth in the clinical trial agreement (CTA) governing [Study site or Investigator] participation in the study. These requirements include, but are not limited to, submitting proposed publications to BMS at the earliest practicable time prior to submission or presentation and otherwise within the time period set forth in the CTA.

